# 10.5 Collecting and Reporting procedure

# 10.5.1 Adverse Events

Care home staff will report all events that meet the definition of an AE other than those events that do not require reporting (see section 10.6). The care home staff should manage those events excluded from reporting according to routine care home procedures. If an adverse event has occurred, the care home staff should inform the trial staff immediately or during the regular monthly data collection visit. The trial staff will collect and report the data directly into the CRF paper form specific for recording AEs (HRA/Non-CTIMP safety report to REC form) and into the ELDER Monthly Record.

#### 10.5.2 Serious Adverse Events

All SAEs will be collected as part of a routine monthly follow-up (recorded by the trial staff on the ELDER Monthly Record under a separate subheading 'Further Comments – CRF Information' and into an SAE form (HRA/Non-CTIMP safety report to REC form) from the time of consent until the 9-month follow-up period). The delivery staff will discuss SAEs with a second delegated assessor (CTC from the coordinating centre) to confirm the causality classification (definitely, probably, possibly, unlikely, not related). The details of the second assessment will be reported on the ELDER Monthly Record under Further Comments – CRF Information. If the two assessors have assigned a different classification for an event assessed, then the highest category of causality (most likely to be related) will be selected, and the CI will confirm the assessment.

[figure not shown]
#### 10.5.3 Serious Adverse Reaction

An SAE classified by the delivery staff/CTC and further confirmed by the CI as being probably or definitely related to the study product (diagnostic tests confirming septicaemia or the suspected pathogen is identified as the Bacillus strain used in the ELDER study product) will be classed as a SAR. In such cases, the trial staff should complete a purpose-designed SAR form, and the original

form returned to CTC within four days of the trial staff becoming aware of these events. The trial staff completing the report should include a detailed explanation of the event and supplement the report with clinical test results; if the hospital reports are not available at the time of reporting, the trial staff should forward the follow-up information as soon as possible to CTC, who would include these additional data in the appropriate report. Related and unexpected SAEs (i.e., all unexpected SARs) will be reported to the REC within 15 days of the CI/CTC becoming aware of the event. The CTC is responsible for additionally reporting SARs to the monitoring committee and the study product manufacturer (SACCO Systems) as appropriate.

Contact details for reporting SARs
Please Email to [contact], attention Clinical Trial Coordinator
Queries
[contact] (Mon to Fri 09.00 – 17.00)

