# 8. Trial Intervention

The consented care homes will be assigned randomly to one of the study arms: - (a) Group 1: non-supplemented milk (placebo), (b) Group 2: milk supplemented with fluoride (5.0 mg F/l), (c) Group 3: milk supplemented with probiotics (Lactobacillus), and (d) Group 4: milk supplemented with fluoride and probiotics. All subjects will be asked to drink a glass of plain/supplemented milk once daily, five days a week, for nine months. Fluoridated milk or probiotics, or placebo (referred to as the Study product) will be administered by the resident's routine caregiver during medicinal/meal rounds. The study product will be sourced from the manufacturer and transported to the study site. Fluoridated milk will be distributed in a small carton, and the probiotics will be provided as a powder in sealed sachets. The preferred route of administration is as follows:

1. The carton containing fluoridated milk is to be emptied into a tall glass and then consumed.

2. The probiotic powder is to be dispensed in a spoon, then added to a prepared glass of skimmed milk/fluoridated milk, mixed well and then consumed

Each care home will be provided with the manufacturer's dossier detailing the composition of the probiotic form and fluoridated milk. After allocation, probiotic sachets will be distributed to the care home at the beginning of the trial, whereas milk (both skimmed & fluoridated) will be distributed to the trial sites weekly. Participants admitted to the hospital would not be expected to continue taking the study product during their hospital stay.

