#### 10.3.1. Summary of current manufacturer's information

SACCO System's safety information sheet published in 2016 states that the probiotic product *Lactobacillus rhamnosus* is not hazardous and is well tolerated even among children aged 1-5 years. Rare cases of secondary infection have been reported in immunosuppressed patients, but since the trial excludes residents with any immune compromised medical condition, we, therefore, do not expect any adverse events based on the current manufacturer's information.

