# 10.4 Reporting Period

The adverse event reporting period for this study begins as soon as the resident provides informed consent and ends one month after the final data collection. The study products (probiotics and fluoridated milk) being used in this trial is a well-established food supplement, and given the frailty of the study population with a wide range of healthcare needs, it's critical not to cloud any true emerging safety signals by collecting unrelated data. Therefore, safety reporting in this study will focus on SAEs that could be related to the study population, and only SARs that could be related to the study product will be assessed for expectedness. The onset of any AE will be apparent particularly to care home staff, as they know their residents and their medical conditions thoroughly and so can quickly identify any deterioration to a resident's health very early. The care home staff will be informed of the pre-specified events that could be expected with the study.

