# **SAE SAFETY REPORTING FLOWCHART**

# 10.6 Events that do not require reporting

The study population will have a vast number of health events in the normal course of their care at this stage of life, and therefore it's important to distinguish between reporting events that could be connected with the trial intervention and those events that are frequently occurring in care homes and are unrelated. Such events which deemed unrelated to the study and will not be reported as AEs or SAEs, and these include:

- Agitation
- Allergic reaction (not related to study product)
- Anorexia, loss of appetite
- Bruising, ecchymoses
- Confusion
- Delirium
- Dehydration
- Fall with injury, with/without fracture
- Cardio vascular-related events
- Hypoglycaemia
- Hypotension
- Medication (non-trial) error
- Nursing care missed
- Pressure ulcer
- Skin tear, abrasion, breakdown
- Urinary tract infection with catheter

Similarly, pre-existing diseases or conditions present before the intervention that does not worsen will not be included as AE.

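### The SAR rule in 10.5.3, the expectedness sources in 10.3 and the manufacturer notification are written for the probiotic only, although section 8 also makes fluoridated and placebo milk study product

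*Protocol*

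**What the plan says.** Section 8 sets the scope of the term: "Fluoridated milk or probiotics, or placebo (referred to as the Study product"). Its list of arms begins "a) Group 1: non-supplemented milk (placebo), (b) Group 2: milk supplemented with fluoride (5.0 mg F/l"), so Groups 1 and 2 take no probiotic; Group 4 takes fluoride and probiotic together. Section 10.4 repeats that fluoridated milk is included: "The study products (probiotics and fluoridated milk) being used in this trial".

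Section 10.1 calls any SAE thought probably or certainly related to the study product a SAR. The causality table in 10.2 also refers to the study product without singling out a component.

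Section 10.3 says that expected events will be taken from manufacturing information and evidence on the study product. Section 10.3.1 then summarises one safety sheet, from SACCO, which "states that the probiotic product" *Lactobacillus rhamnosus* is not hazardous. Section 10.3.2 summarises literature on probiotics.

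Section 10.5.3 repeats the probable-or-definite threshold and adds in brackets "diagnostic tests confirming septicaemia or the suspected pathogen is identified as" the Bacillus strain of the study product. It sets the four-day SAR form and the 15-day report to the research ethics committee (REC), and gives the coordinator the further task of "additionally reporting SARs to the monitoring committee and the study product manufacturer (SACCO Systems) as appropriate".

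Section 10.6 exempts from reporting "Allergic reaction (not related to study product").

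**The concern.** The term is defined broadly, but three working rules that depend on it are filled in for one component only: what counts as a reaction, what counts as expected, and which manufacturer is told.

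This matters because the SAR label triggers the four-day form, the 15-day REC report, the line listing to the Data Monitoring Committee (15.5) and the manufacturer notification. The SAR reporting note at the front of the protocol sends staff to section 10.5, where the narrower wording sits, and not to 10.1. The people who classify (delivery staff and the coordinator, 10.5.2) know the allocation (6.5). If some read the parenthesis as a condition and others as an illustration, similar events could be labelled differently between homes, and therefore between arms, since the home is the unit of randomisation.

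**Working it through.** There is no stated figure to reproduce; the check sets the sections against each other.

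**1. SAR criterion.** The protocol does not say whether the 10.5.3 parenthesis is an example or a condition. Take three hypothetical SAEs, each judged probably related:

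| Event | Under 10.1 and 10.2 | 10.5.3, parenthesis as example | 10.5.3, parenthesis as condition |
|---|---|---|---|
| Serious allergic reaction to milk, any arm | SAR | SAR | not a SAR |
| Serious gastrointestinal reaction, Group 2 | SAR | SAR | not a SAR |
| Confirmed septicaemia, any arm | SAR | SAR | SAR |

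The first two rows change with the reading. Other sections are hard to square with the conditional reading:

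- 10.3.2 provides for gastrointestinal symptoms that meet the SAR definition and calls them unexpected in that case. That provision would have little purpose if only septicaemia or a strain identification could qualify.
- 10.6 exempts allergic reactions only when they are unrelated to the product, so related ones stay reportable.

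**2. Organism.** The strain limb names Bacillus. Section 8 says Lactobacillus and 10.3.1 says *Lactobacillus rhamnosus*. Taken literally, the limb refers to an organism that no other section places in the product.

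**3. Expectedness.** Section 10.3 promises information on the study product; 10.3.1 and 10.3.2 supply it for the probiotic. Nothing is given for fluoridated or plain milk. Classification does not fail, however: 10.1 treats an event type not listed in the protocol as unexpected, in every arm.

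**4. Notification.** SACCO Systems is the only manufacturer named, and 10.3.1 ties it to the probiotic. No route to the supplier of the fluoridated or plain milk is stated.

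**5. How many residents.** Target 240 (11.1), four arms (3), allocation 1:1 with blocking meant to balance participant numbers (6.4):

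- per arm: 240 / 4 = 60
- on fluoridated milk (Groups 2 and 4): 2 × 60 = 120
- nominal exposure over nine months: 120 × 0.75 = 90 person-years

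This assumes equal arms, full recruitment, no attrition and nine months for everyone. It counts residents covered by the gap. It does not estimate misclassified events, for which the protocol gives no rate.

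**The case against.** The strongest reply is that a usable criterion already exists in every arm. Section 10.1 is generic, 10.2 is generic, and under 10.5.2 two assessors classify, the higher causality category prevails and the chief investigator confirms. Sections 10.3.2 and 10.6 suggest that the parenthesis was meant as an illustration. This stands, and it limits the point.

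A reader might infer that homes in Groups 1 and 2 can never record a SAR, so that the count there is zero by construction. The documents do not support that: besides the generic definition, the septicaemia limb is not tied to any strain. Nor do they show that such reactions must miss the REC report. With no list for milk or fluoride, a related SAE is unexpected by default, which favours reporting. Apart from the 10.6 exemptions, SAEs are collected monthly whatever their cause (10.5.2), and the Data Monitoring Committee sees AE data as well as SAR listings (15.5). It would also go too far to speak of a distorted safety comparison between arms: SARs are not an endpoint in 2.4, and 11.2 confines intervention effects to description.

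The words 'as appropriate' in the notification clause leave some discretion, but they name no second manufacturer. The SAR form and the safety flowchart could carry clearer wording; the protocol text examined does not show it.

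What the reply does not remove is that the section staff are sent to is narrower than the definition it applies, names a different organism, and relies on reference information for one component.

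**Conclusion.** The point holds as an inconsistency that should be corrected. The 10.5.3 parenthesis conflicts with 10.1, 10.3.2 and 10.6 if read as a requirement, and the text does not exclude that reading. The organism name contradicts sections 8 and 10.3.1 on any reading. The missing reference information and notification route are gaps against the protocol's own definition of study product; for fluoride they concern Groups 2 and 4, about 120 residents under the assumptions above. The fluoride gap is therefore not confined to the arms without probiotic.

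The consequence is a risk that serious milk or fluoride reactions are classified inconsistently and are not passed to the relevant supplier. How often this would happen cannot be derived from the documents.

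**What to change.** - **10.5.3, parenthesis:** reconcile it with 10.1 by stating that the microbiological findings are examples for the probiotic arms (Groups 3 and 4). Keep the existing probable-or-definite threshold; widening it to any related SAE would change the rule instead of reconciling it.
- **10.5.3, organism:** reconcile the name with sections 8 and 10.3.1.
- **10.3:** add reference information for fluoridated and plain milk, so that the section matches the section 8 definition. The manufacturer's dossier mentioned in section 8 is described as covering composition, so the sponsor should check whether it holds safety information before relying on it.
- **10.5.3, notification:** extend it to the manufacturer of whichever component the resident took.

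The cost is a wording amendment, the work of obtaining the milk information, and possibly a few more events classed as SARs. Design, sample size and analysis do not change.

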# **SAE SAFETY REPORTING FLOWCHART**

# 10.6 Events that do not require reporting

The study population will have a vast number of health events in the normal course of their care at this stage of life, and therefore it's important to distinguish between reporting events that could be connected with the trial intervention and those events that are frequently occurring in care homes and are unrelated. Such events which deemed unrelated to the study and will not be reported as AEs or SAEs, and these include:

- Agitation
- Allergic reaction (not related to study product)
- Anorexia, loss of appetite
- Bruising, ecchymoses
- Confusion
- Delirium
- Dehydration
- Fall with injury, with/without fracture
- Cardio vascular-related events
- Hypoglycaemia
- Hypotension
- Medication (non-trial) error
- Nursing care missed
- Pressure ulcer
- Skin tear, abrasion, breakdown
- Urinary tract infection with catheter

Similarly, pre-existing diseases or conditions present before the intervention that does not worsen will not be included as AE.

#### 11. Statistical considerations

# 11.1 Sample size

The sampling frame adopted for this study is a non-random convenience sampling, depending on the availability within the 3-month recruitment window and their acceptance to participate in the study. This pilot RCT is not powered to detect intervention effects. The size of the study is sufficient to address the primary feasibility outcomes of acceptability of/compliance with the intervention and whether the potential oral health outcomes for a subsequent definitive trial can be captured robustly. The aim is to recruit up to 10 care home residents per home (a minimum of four and a maximum of fifteen) from care homes resulting in an estimated recruited sample of 240. This calculation was based on the calculations of a four-arm trial with three experimental treatments, with a normally distributed outcome, a standardised value of 0.6 being considered an interesting treatment effect, a significance level of 0.05, and Bonferroni's correction for multiple testing. The sampling size estimation was based on the required number of clusters (care homes) with an average consenting participant of 10.

#### 11.2 Analysis of Outcome Measures

The proportion of participants complying with the interventions together with the Clopper-Pearson 95% confidence interval will be assessed. We shall apply generalised linear mixed modelling with

distribution and link function matching the outcome variable in question. Mean intervention effects will be presented with 95% confidence intervals for descriptive purposes only, with no inferences made regarding efficacy, as appropriate for a pilot.

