# 2.4 Outcome Measures

The primary endpoints will be:

- i. Acceptability of the supplemented milk and compliance with the intervention programme
- ii. Potential clinical dental results of the intervention, including root caries and gingival inflammation
- iii. Bacterial and fungal counts in saliva and supragingival plaque at baseline and over a subsequent 9-month period

The secondary endpoints will be:

- i. Frequencies of infection
- 1. Use of antibiotics and unscheduled pain killers
- 2. Urgent care appointments (medical/dental) over the 9-month period of intervention

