#### 6.4 Randomisation

The unit of randomisation is the care home (cluster). The care homes will be randomised based on a 1:1 ratio to each available intervention arm or control arm. Trial staff at each trial site will inform the coordinating centre when there are four eligible care homes as they will be randomised in a set of four or six if two sister care homes belonging to the same chain are recruited. As the unit of randomisation is a care home, and the number of participants in each care home is expected to vary, blocking will be used to ensure a close balance of the number of participants (and not necessarily care homes) assigned to each arm. The allocation for a particular trial site will only be revealed after gaining informed consent (i.e., both at the care home level and the individual participant level) and baseline data collection. This approach reduces the threat of post-randomisation selection bias in cluster trials, as individual participants consent to be randomised to one of the four arms rather than being told which arm they have been allocated to if consent is only sought at the level of the care home.

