# 8.2 Acceptability and Compliance

A critical outcome is compliance with the intervention programme. We define compliance as consumption of the allocated milk on >50% of intervention days. This threshold approximates consuming the milk four in every seven days and is based on the implementation of milk fluoridation schemes in schools, where milk is provided only on school days which constitute approximately 53% of a calendar year. We define success with respect to compliance if 75% of the sample meets this criterion. Consumption of assigned milk will be assessed using a consumption sheet collected from the participants.

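### The compliance interval named in section 11.2 ignores care-home clustering, so it will overstate precision if compliance is correlated within homes

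*Protocol*

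**What the plan says.** Section 2.4 lists as the first primary endpoint "Acceptability of the supplemented milk and compliance with the intervention programme". Section 8.2 makes compliance a yes/no outcome for each resident: "We define compliance as consumption of the allocated milk on >50% of intervention days". It then sets the target: "We define success with respect to compliance if 75% of the sample meets this criterion". For the analysis, section 11.2 names one method: "The proportion of participants complying with the interventions together with the Clopper-Pearson 95% confidence interval will be assessed". The following sentences of 11.2 introduce generalised linear mixed models matched to the outcome, and then intervention effects with 95% intervals for description only.

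On the design, section 6.4 makes the care home the unit of randomisation. Under section 8 the study product "will be administered by the resident's routine caregiver during medicinal/meal rounds", and milk reaches the homes weekly. Section 11.1 works with about 10 residents per home, "resulting in an estimated recruited sample of 240". Section 4 allows 4 to 15 residents per home and mentions five in each home where sister homes of one chain take part. No ICC, design effect or number of homes is stated.

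**The concern.** Clopper-Pearson inverts a single binomial distribution and is valid when the residents' outcomes are independent. Residents of one home share an allocation, a weekly delivery, a routine and the staff who hand out the milk. Whether a resident drinks it on more than half of the days depends partly on these shared conditions, so a positive within-home correlation is likely. In that case 240 residents carry less information than 240 independent people, and an interval that counts them as independent claims too much.

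The issue is not a detail that can be left to an analysis plan, because the protocol itself fixes the method by name. Section 11.1 says the trial is not powered for intervention effects but is large enough for the feasibility outcomes, with compliance among them. The precision reported for compliance is therefore one of the main things this pilot hands to the planners of a definitive trial.

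**Working it through.** **Inputs from the protocol.** Total sample 240 and an average of 10 residents per home (11.1); 4 to 15 per home, or five per sister home (4); 75% compliance as the reference value (8.2); Clopper-Pearson at 95% (11.2).

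**Assumptions.** ICC of 0.01 to 0.20. Number of homes: 240/10 = 24 as the main case, 240/5 = 48 as a favourable one.

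**The plan's own figure.** Section 11.1 derives 240 from a standardised effect of 0.6 with Bonferroni correction; power and sidedness are not stated. Assuming two-sided testing at 0.05/3 and 80% power, n per arm = 2(2.394 + 0.842)²/0.6² = 58.2, so 59, and 4 × 59 = 236, close to 240. This match contains no inflation for clustering. Other settings also give 236 (unadjusted two-sided 0.05 at 90% power, for example), so it shows only that 240 can be reached without a design effect. It is not a precision calculation for compliance.

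**Step 1: the interval as planned.** At 75% compliance, 180 of 240. The lower limit is the 2.5% quantile of Beta(180, 61) and the upper limit the 97.5% quantile of Beta(181, 60). Result: 69.0% to 80.3%, width 11.3 points.

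**Step 2: allowing for home.** Design effect DE = 1 + (m − 1) × ICC, effective sample n_eff = 240/DE, and Clopper-Pearson on 0.75 × n_eff out of n_eff. With m = 10:

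| ICC | DE | n_eff | Interval | Width against plain |
|---|---|---|---|---|
| 0.01 | 1.09 | 220.2 | 68.7-80.6% | 1.05 |
| 0.05 | 1.45 | 165.5 | 67.7-81.4% | 1.21 |
| 0.10 | 1.90 | 126.3 | 66.5-82.3% | 1.39 |
| 0.20 | 2.80 | 85.7 | 64.5-83.7% | 1.70 |

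**Step 3: coverage of the plain interval.** Beta-binomial simulation with true compliance 75%, counting how often the nominal 95% interval contains 75%:

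| ICC | 24 homes of 10 | 48 homes of 5 |
|---|---|---|
| 0.01 | about 95% | about 95% |
| 0.05 | about 91% | about 93.5% |
| 0.10 | about 86% | about 91% |
| 0.20 | about 77% | about 87% |

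At ICC 0.01 the built-in conservatism of Clopper-Pearson roughly offsets the clustering. The 48-home column treats sister homes as independent of each other, which favours the plain interval.

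**Step 4: unequal homes.** If sizes were spread evenly over 4 to 15, the coefficient of variation would be about 0.363. With DE = 1 + ((1 + CV²) × 10 − 1) × ICC, the design effect at ICC 0.10 is 1 + (1.132 × 10 − 1) × 0.10 = 2.03 instead of 1.90, which is slightly worse.

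**Step 5: one arm.** With 45 of 60 (six homes of 10, assumed) the plain interval is 62.1-85.3%. The adjusted one is 56.5-88.6% at ICC 0.10 and 51.8-90.9% at ICC 0.20.

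**The case against.** The strongest reply is that little turns on this interval. A reader might infer that it decides whether the compliance target is met, and so whether a definitive trial follows. The protocol does not support that. Section 8.2 sets a criterion on the observed proportion and names no confidence limit, and no section ties progression to the interval. A wider interval leaves both the estimate and the verdict on 75% as they are. This stands, and it limits how serious the point is.

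A second reply is that the interval cannot be called too narrow without an ICC. This also stands: near ICC 0.01 there is practically no loss, and with smaller homes the loss is milder. Drinking the milk also depends on the resident, not only on the home. But delivery by staff makes a negligible correlation hard to presume, and an adjusted interval costs little if the correlation does prove small.

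A third reply is that the mixed models in 11.2 could include compliance. Their wording does not exclude it, and it would be wrong to say that they serve intervention effects only. Still, the text does not say that the compliance interval comes from such a model, and a Clopper-Pearson interval carries no home effect.

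Finally, this is a pilot with a convenience sample, so any coverage figure is model-based. The descriptive-only caveat in 11.2, however, is attached to intervention effects and not to compliance.

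**Conclusion.** The point holds conditionally. Section 11.2 fixes an independence-based interval for a clustered primary endpoint. If compliance is positively correlated within homes, which delivery by home staff makes likely, the interval is too narrow and its coverage falls below 95%. With 24 homes of 10, the loss runs from almost nothing at ICC 0.01 to about 18 percentage points at ICC 0.20 (95% − 77%). With 48 homes of 5 it is about 8 points at ICC 0.20 (95% − 87%). These figures rest on an assumed ICC, an assumed number of homes and true compliance of 75%. What is overstated is the precision around the main feasibility estimate; the estimate and the success rule are unaffected. It should be fixed, but it does not put the trial's feasibility verdict at risk.

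**What to change.** In section 11.2, replace the plain Clopper-Pearson interval for the overall compliance proportion with one that accounts for care home. Either of these would do:

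- Clopper-Pearson on the effective sample size, with the variance estimated between homes and t quantiles on homes minus one (the Korn-Graubard method).
- A home-level ratio estimate with robust variance and t quantiles.

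In simulation with 24 homes of 10, at ICC 0.05 to 0.20, the first covered about 96% and the second 94-95%.

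Report the compliance ICC next to the interval; this serves objective 3 in section 2.3, which asks for variability to plan the definitive trial. If intervals are also given by arm, use the same method and state that the few homes per arm make them imprecise.

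The change takes about one sentence in the protocol and a few lines of code. Recruitment, data collection and the 75% criterion stay as they are. The downside is a wider interval.
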